12.1.1 Sensitivity analysis of the primary endpoint

Imputation of missing data

To assess the impact of missing data, sensitivity analysis using the multiple imputation approach will be applied. All missing data will be assumed to be missing at random (MAR). The imputation will consider and use only LEROS data, since the matched external natural history control group is not longitudinal data and does not include any missing data. The VA assessments from all visits up to Month 12 will be used. First the MCMC methodology will be applied to impute the data to obtain monotonously missing data. Then imputation will be completed using regression imputation for the monotonously missing data. CRB will be defined based on the imputed VA data. Analysis model will be run for the imputed 12-month data by imputation and SAS procedure *mianalyze* will be used to calculate the combined results.

```
SAS code to perform multiple imputation on missing visual acuity results assuming MAR (values: Raxone® treated patients = 1; NH = 0)
```

```
/* STEP 1: LEROS data imputation*/
```

/*impute non-monotonously missing observations */

proc mi data=visual acuity out=visual acuite monotone nimpute=1000 seed=xxx;

var v2logMAR v3logMAR v4logMAR v5logMAR v6logMAR;

mcmc chain=multiple impute=monotone;

run;

/*use regression imputation to complete MAR imputation*/

proc mi data= visual_acuite_monotone out=visual_acuite_imputed nimpute=1 seed=xxx;

var v2logMAR v3logMAR v4logMAR v5logMAR v6logMAR;

monotone regression;

run;

* STEP 2: calculation of visit 6 CRB from baseline for imputed values visit 6 CRB from baseline should be calculated with the same SAS code used for the main analysis of the primary endpoint

input dataset: visual_acuite_imputed;

SNT-IV-005 Statistical Analysis Plan

Confidential

V1.0 07 June 2021

```
calculate LEROS visit 6 CRB;
             output dataset: leros crb imputed
     STEP 3: repeat 1000 times Natural History data used the main analysis of the
              primary endpoint and join with LEROS data set which has the imputed CRB calculation*/
data natural history repeated;
  set natural_history_analysis data;
    do _Imputation_ = 1 to 1000;
       output;
    end;
  run;
data all_data_joined;
       set leros_crb_imputed natural history repeated;
run;
     STEP 4: applying logistic model over the new imputed CRB data*/
proc sort data= all_data_joined; by Imputation; run;
proc logistic;
   by Imputation;
  class treatment gender mutation / param=ref;
  model CRB(event='1') = treatment gender mutation / link=logit clodds=pl;
  ods output ParameterEstimates = ParameterEstimates;
  ods output CLOddsPL = CLOddsPL;
run;
     STEP 5: calculate the logistic analysis combined results*/
proc mianalyze parms(classvar=classval)= ParameterEstimates.;
   modeleffects treatment gender mutation;
run;
```

```
STEP 6: calculate the combined results odds ratio */
/* Transform estimates */
data calculated odds ratio 1;
   label or_value = 'Log odds ratio value'
        or stderr = 'Log odds ratio SE';
  set CLOddsPL;
     or value = log(OddsRatioEst);
     or_stderr= (log(uppercl)-log(lowercl))/(2*1.96);
run;
    Combine transformed estimates */
proc sort data= calculated_odds_ratio_1; by Effect; run;
proc mianalyze data= calculated_odds_ratio_1;
       by Effect;
       modeleffects or_value;
       stderr or_stderr;
       ods output ParameterEstimates = calculated odds_ratio_2;
     run;
     Back-transform combined values */
data calculated odds ratio 3;
   label estimate back = 'Odds ratio'
        lcl back = 'LCL Odds ratio'
        ucl_back = 'UCL Odds ratio';
       set calculated_odds_ratio_2;
       estimate back = exp(estimate); *pooled odds ratio;
       lcl_back=estimate_back*exp(-1.96*stderr); *pooled lower limit;
       ucl_back=estimate_back*exp(+1.96*stderr); *pooled upper limit;
     run;
```

Through inverse probability of treatment

Propensity score will be calculated by means of logistic regression with treatment as dependent variable. Independent variables include gender (male, female), mutation group (G11778A, G3460A, T14484C), age, time since symptoms onset in months and VA at BL (logMAR) as factors.

The same primary model as described above will be applied with the inverse probability weight.

```
SAS code to calculate the propensity score (values: Raxone® treated patients = 1; NH = 0)
proc logistic data=CRB dataset;
  class gender mutation / param=ref;
  model treatment(event='1') = gender mutation age time onset bl va;
  output out=psdataset pred=ps;
run;
data analysis dataset;
  set psdataset;
  if treatment = 1 then ps weight = 1/ps;
  else if treatment = 0 then ps weight = 1/(1 - ps);
run;
SAS code to proceed with the endpoint regression analysis
proc logistic data= analysis dataset;
  class treatment gender mutation / param=ref;
   model CRB(event='1') = treatment gender mutation / link=logit clodds=pl;
  oddsratio treatment;
  weight ps_weight;
run;
```

Effect of the size of time window used in the matching

The effect of the size of time window used in the matching algorithm can be explored rerunning the algorithm and primary analysis using different time windows

- VA assessments within 12±3.5 months from BL
- VA assessments within 12±4 months from BL

The same primary model as described above will be applied.

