For the missing data assuming MAR, the multiple imputation approach will be applied. The imputation will consider and use only LEROS data, since the matched external natural history control group is not longitudinal data and does not include any missing data. As the disease does not progress linearly, only the 12 month (Visit 6) and 18 month (Visit 7) data will be used for the imputations. First the MCMC methodology will be used to impute the data to obtain monotonously missing data. Then imputation will be completed using regression imputation for the monotonously missing data. Analysis model will be run for the imputed data by imputation and SAS procedure *mianalyze* will be used to calculate the combined results.

SAS code to perform multiple imputation on missing visual acuity results assuming MAR:

/* STEP 1: LEROS data imputation*/

/*impute non-monotonously missing observations */

proc mi data=visual acuity out=visual acuite monotone nimpute=1000 seed=xxx;

var logMAR_v6 logMAR_v7 logMAR_v8;

```
mcmc chain=multiple impute=monotone;
run;
/*use regression imputation to complete MAR imputation*/
proc mi data= visual_acuite_monotone out=visual_acuite_impute=1 seed=xxx;
  var logMAR_v6 logMAR_v7 logMAR_v8;
  monotone regression;
run;
    STEP 2: calculation of visit 8 CRB from baseline for imputed values
             visit 8 CRB from baseline should be calculated with the same SAS code
             used for the main analysis of the primary endpoint but use visit 8 as main variable
             input dataset: visual acuite imputed;
             calculate LEROS visit 8 CRB;
             output dataset: leros crb imputed
*/
    STEP 3: repeat 1000 times Natural History data used the main analysis of the
             primary endpoint and join with LEROS data set which has the imputed CRB calculation*/
data natural history repeated;
  set natural history analysis data;
    do Imputation = 1 to 1000;
       output;
    end;
  run;
data all data joined;
        set leros crb imputed natural history repeated;
run;
    STEP 4: applying logistic model over the new imputed CRB data*/
proc sort data= all_data joined; by Imputation; run;
proc logistic;
   by _Imputation_;
```

```
class treatment gender mutation / param=ref;
   model CRB(event='1') = treatment gender mutation / link=logit clodds=pl;
   ods output ParameterEstimates = ParameterEstimates;
   ods output CLOddsPL = CLOddsPL;
run;
     STEP 5: calculate the logistic analysis combined results*/

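### The imputation code for the primary endpoint omits baseline VA, which its text includes, leaves out mutation and gender, and runs its second step without a BY statement

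*SAP*

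**What the plan says.** SAP 12.1.1 imputes missing LEROS acuity under a missing-at-random assumption. On the inputs the text says "The VA assessments from all visits up to Month 12 will be used". Protocol 6.2 schedules VA at Visit 1 (Baseline) and at every later visit; Visit 6 is Month 12.

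The code runs in two imputation steps, and both list "var v2logMAR v3logMAR v4logMAR v5logMAR v6logMAR".
- The first step makes 1000 copies with "mcmc chain=multiple impute=monotone", which fills only the gaps that prevent a monotone pattern.
- The second step is "proc mi data= visual_acuite_monotone out=visual_acuite_imputed nimpute=1 seed=xxx". Only the VAR line and a monotone regression line follow it.

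CRB from baseline is then derived from the imputed acuity. The control data are copied under "do _Imputation_ = 1 to 1000". The text says "Analysis model will be run for the imputed 12-month data by imputation", and the model is "model CRB(event='1') = treatment gender mutation / link=logit clodds=pl".

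SAP 16 makes CRB the composite of recovery and stabilisation. The first is an improvement, counted from baseline in the primary endpoint. The second applies only to eyes better than 1.0 logMAR at baseline. Protocol 1.2 describes the causative mutation as prognostic for recovery.

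SAP 12.4 uses the same two-step code for Month 24 with "var logMAR_v6 logMAR_v7 logMAR_v8". Its text gives a reason for using only Visits 6 and 7 as inputs: the disease does not progress linearly.

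**The concern.** There are three separate problems.

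1. **Baseline VA.** Month 12 acuity is imputed without the value it is then compared with. Here the code departs from its own text.
2. **Mutation and gender.** The imputation model holds less than the analysis model. An eye that drops out is imputed as if nothing were known of its mutation beyond what its early visits show. Carriers of a good-prognosis mutation are then imputed too low and the others too high.
3. **No BY statement.** The second step sees one long data set instead of 1000 separate ones. Its regression parameters are therefore not redrawn for each copy, and the between-imputation variance is too small.

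The plan expects 30% drop-out. Protocol 9.4.2 had planned a generalized linear mixed model to assess incomplete data, with factors similar to those of the primary model. The SAP does not carry that model forward. The analysis in 12.1.1 is therefore the only check the SAP offers on missing data for the primary endpoint.

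**Working it through.** **1. Number of imputed eyes.** Protocol 9.6 and SAP 6 need 110 evaluable eyes and allow for 30% drop-out. 110 / (1 − 0.30) = 157.1, rounded up to 158 eyes or 79 patients, against the 80 patients (160 eyes) stated. The figure reproduces. About 0.30 × 160 = 48 eyes would need imputation.

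**2. Code against text.**

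| Item | Text of 12.1.1 | Code of 12.1.1 | Finding |
|---|---|---|---|
| VA inputs | all visits to Month 12 | Visits 2–6 | Visit 1 missing: mismatch |
| Mutation, gender | silent | absent from imputation, present in analysis model | weaker model, no contradiction |
| Second step | monotone regression to complete the data | one run on 1000 stacked copies, no BY | parameters not redrawn per copy |

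A line lost in reading the PDF is unlikely. BY lines survive elsewhere in the same listing, and this one is absent in both 12.1.1 and 12.4.

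**3. Why the second step matters.** For an eye that simply stops attending, the pattern is already monotone and the first step fills nothing. All imputation of drop-out eyes then happens in the step without BY.

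**4. Simulation.** Each simulated trial had 160 LEROS eyes and 175 control eyes (the control count in SAP 6), about 30% monotone drop-out and 30 imputations; there were 120 to 150 trials per setting. The documents do not give the mutation mix, VA courses or timing of drop-out, so these are assumptions. Three versions were compared:
- A: Visits 1–6 plus mutation and gender, fitted per imputation.
- B: Visits 2–6 only, fitted per imputation.
- C: Visits 2–6 only, fitted once to the stacked copies, index assumed kept.

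Response rate among drop-out eyes, range over all settings:

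| Mutation | True | A | B and C |
|---|---|---|---|
| T14484C | 0.82–0.84 | 0.80–0.83 | 0.53–0.73 |
| G3460A | 0.37–0.41 | 0.37–0.41 | 0.43–0.51 |
| G11778A | 0.43–0.45 | 0.44–0.45 | 0.47–0.53 |

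Treatment log odds ratio:

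| Drop-out, T14484C vs other mutations | Full data | B | C | Shift, B or C minus full data |
|---|---|---|---|---|
| 30% vs 30% (three timings) | 0.281, 0.287, 0.299 | 0.293, 0.288, 0.297 | 0.295, 0.286, 0.298 | within 0.02 |
| 14% vs 34% (two timings) | 0.273, 0.276 | 0.351, 0.337 | 0.348, 0.334 | +0.06 to +0.08 |
| 60% vs 22% (two timings) | 0.301, 0.316 | 0.184, 0.232 | 0.184, 0.233 | −0.08 to −0.12 |

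Version A stays within about 0.01 of full data throughout. The pooled standard error is about 0.25, so the largest shift is about 0.12 / 0.25 = 0.5 standard errors. On the odds-ratio scale the shifts run from exp(−0.12) = 0.89 to exp(0.08) = 1.08 times the full-data value.

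**5. Effect of the missing BY alone (B against C).** Pooled SE = √(W + (1 + 1/M)B), where W and B are the within- and between-imputation variances and M = 30. With equal drop-out spread evenly over visits:
- version B: √(0.0543 + 1.03 × 0.00692) = 0.248
- version C: √(0.0543 + 1.03 × 0.00572) = 0.245

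That is 1.0% lower (0.2478 to 0.2453). Over all settings the between-imputation variance falls by 11–21% and the pooled SE by 0.6–1.5%.

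**6. If the second step resets the index to 1.** Group 1 would hold 1000 copies of every LEROS eye. Groups 2 to 1000 would hold controls only, and no treatment effect could be estimated in them. The documents do not say how the procedure treats an existing index, so this is a conditional result.

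**The case against.** The strongest reply is that little depends on this code. It serves a sensitivity analysis whose product is a pooled treatment odds ratio, not response rates by mutation. That odds ratio barely moves unless drop-out depends on mutation, and the documents give no sign that it does. Post-baseline acuity already carries part of the information in baseline VA and mutation. The listing is also a sketch: the seed is a placeholder and the CRB step is only a comment, so the final program may differ.

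Most of this stands, and it limits the size of the point. It does not remove the mismatch on baseline VA, and a listing printed in a SAP is what a programmer will follow.

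Four stronger readings are tempting, and the documents do not support them.
- **The primary result is biased.** SAP 12.1 uses only eyes with a Month 12 assessment, so this code does not touch it.
- **The code contradicts the text on mutation and gender.** The text never says they will be imputation predictors.
- **Carriers as a whole are badly misclassified.** A simpler simulation assumed 20% carriers of a better-prognosis mutation gaining 0.45 logMAR, and gave 51–55% as coded against a true 72–75%. That gap concerns imputed carrier eyes only: 160 × 0.20 × 0.30 = 9.6 eyes, so about 2 eyes change status. With a gain of 0.2 logMAR it falls to 6–12 points, about one eye.
- **SAP 12.4 repeats the baseline error.** There the restriction to Visits 6 and 7 is stated and reasoned, and the code follows it.

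**Conclusion.** The point holds as a mismatch between code and text, and as a weakness of specification, in the SAP's only missing-data analysis of the primary endpoint. The omission of baseline VA contradicts the text. The omission of mutation and gender makes the imputation model poorer than the analysis model. The missing BY understates imputation uncertainty slightly, and would make the by-imputation steps fail only if the index is also reset.

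The expected effect on the treatment log odds ratio is negligible (0.02 or less) when drop-out is unrelated to mutation. It is modest (about 0.06 to 0.12, in either direction) under the assumed mutation-related drop-out. The distortion of response rates by mutation is larger, but confined to imputed eyes.

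These sizes are illustrative. The simulated full-data log odds ratios were 0.27 to 0.32, whereas the planned rates of 40% and 22% imply ln[(0.40/0.60) / (0.22/0.78)] = 0.86. The shifts should therefore be read as orders of magnitude. The findings on the code itself need no such assumptions.

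**What to change.** In SAP 12.1.1:
- Add `v1logMAR` and 0/1 indicators for mutation (two) and gender (one) to the VAR lists of both PROC MI steps. Place them before `v2logMAR`, because complete variables must come first for a monotone pattern. Indicators are preferable to class variables because they also work in the MCMC step. Do not impute within mutation groups, which would be small.
- Add `by _Imputation_;` to the second PROC MI.
- Name these predictors in the text, so that text and code agree.

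In SAP 12.4, add the same BY statement and the mutation and gender indicators. Limiting post-baseline VA to Visits 6 and 7 is a stated choice and can remain; adding baseline VA there is optional.

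The cost is a few lines of code and one sentence of text. No new data are needed: baseline VA and demographics are collected at Visit 1, and the mITT population requires a known mutation. A short dry run should confirm that the index runs from 1 to 1000 after the second step.

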As SNT-CRS-002 study was completed (Clinical Study Report version 1.0 dated 15 July 2019), the data collected in the natural history studies has now been checked for the estimate of the responder rate. Based on the combined data from 175 eyes in the two natural history studies (SNT-IR-006 and SNT-CRS-002), the estimated responder rate is below 22%, i.e. lower than the initially expected rate of 24%. Although the determination of the exact responder rate for the natural history studies requires final data from the LEROS study for matching purposes, it is reasonable to assume that the responder rate of the natural history studies is not higher than 22%. The sample size for LEROS study is therefore re-calculated using the same methods as in the original protocol (Version1.0, 29 January 2016). In order to reach a power of 90% for the comparison of the responder rates between the natural history studies (assumed to be 22% instead of 24%) and the LEROS study (assumed to be 40%, as defined in the protocol), evaluable data from altogether 110 eyes from the LEROS study is required. In order to account for a drop-out rate of 30% (as defined in the protocol), at least 80 patients (equal to 160 eyes) will be enrolled to the LEROS study.

The sample size calculation was done with nQuery Advisor version 8.3.

For the sample size for the eye treated >1 year after the onset of symptoms and the corresponding external natural history control group, the aim is to collect VA data from same number of eyes as for the primary objective in order to compare the patients treated ≤1 and >1 year since the onset of symptoms and to compare patients treated with Raxone >1 year since the onset of symptoms with the corresponding natural history control group, assuming sufficient natural history control data can be collected to generate the natural history control group as described in 8.3.2.

Study: SNT-IV-005

V1.0 07 June 2021

7 Statistical hypotheses

The primary aim of the analysis is to show the superiority of Raxone® (patients treated ≤1 year after onset of symptoms) versus matching NH IDE naïve patients in proportion of eyes with clinically relevant recovery of VA from BL or 12 month maintenance of BL VA better than 1.0 logMAR

H₀: Raxone® (patients treated ≤1 year after onset of symptoms) is not superior to matching NH IDE naïve patients in proportion of eyes with CRR of VA from BL or 12 month maintenance of BL VA better than $1.0 \log MAR$

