 H_1 : Raxone® (patients treated ≤ 1 year after onset of symptoms) is superior to matching NH IDE naïve patients in proportion of eyes with CRR of VA from BL or 12 month maintenance of BL VA better than $1.0 \log MAR$

A two-sided 95% confidence interval (CI) for the odds ratio (Raxone® versus NH IDE naïve) is used in the evaluation of the hypotheses. Superiority is shown if the lower limit of the two-sided 95% CI is greater than 1. This is equivalent to obtaining a p-value of less than 0.05 in the statistical test for the H_0 .

8 Analysis sets

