8.5.1 Matching algorithm for the primary endpoint

The external NH control set for the eyes with BL \leq 1 year since onset of symptoms in the LEROS ITT population will be generated as follows (section 19.1 presents the matching algorithms using workflow diagrams and provides examples of matched BL and follow-up visits):

1. Since there is no treatment to be considered in the NH control set, in principle any VA observation at any time point after the onset of symptoms in any eye can be used as a BL for that eye. The primary outcome measure in LEROS is the VA at 12 months after BL. Therefore, using a "window" of ±3 months, any eye with a VA observation at any time point in the NH control set which has a follow-up VA assessment within

SNT-IV-005 Statistical Analysis Plan

Confidential

12±3 months will be retained for use as a possible BL observation. All such possible BL observations and subsequent VA assessments will form the NH control subset to be compared to the BL of LEROS.

- 2. In LEROS, the average time from the onset of symptoms to the start of Raxone® treatment will be calculated once all data is available. The start of the Raxone® treatment will be used as the BL in the statistical analyses.
- 3. For each VA observation retained in the NH control subset, the time from the onset of symptoms at each possible BL time point will be calculated for each eye.
- 4. For each eye in the NH control subset, the VA observation for which time since onset of symptoms is closest to the average time since onset of symptoms at BL calculated for LEROS (see 2) will be selected as the BL VA observation for that eye. Any eye in the NH control subset with a BL VA observation >6 months after the average time since onset of symptoms at BL in LEROS will be discarded. The resulting dataset will form the "final NH control subset" to be used for the primary endpoint. In this way, BL observations in the final NH control subset will be closely matched to the BL in the LEROS ITT population.
- 5. The change from BL in VA at 12±3 months for each eye in the final matched NH control subset will be compared to the change from BL visit to the visit scheduled at Month 12 in LEROS.

This algorithm will guarantee that the time from the onset of symptoms to the BL assessment is comparable between the final NH control dataset and LEROS.

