In the statistical analyses a p-value less than 0.05 will be considered as statistically significant. If not stated otherwise, all tests will be performed as two sided tests and two sided 95% confidence intervals will be produced for the treatment differences.

CRS-1, CRS-2 and LEROS data will be presented in separate listings (one per study).

Unscheduled or repeat assessments in LEROS will not be included in summary tables, but will be included in listings.

Otherwise specified, listings will be sorted by patient number and visit date.

Deviations from the statistical plan will be reported in the clinical study report, including the rationale for the deviation.

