12.1 Primary endpoint

Endpoint: Proportion of eyes with clinically relevant recovery (CRR) of visual acuity from Baseline (BL) or in which BL VA better than 1.0 logMAR was maintained at Month 12 in patients treated with Raxone® ≤1 year after the onset of symptoms, compared to matching external natural history control group. CRR definition is presented in section 16.

Analysis sets: Primary endpoint analysis will use all LEROS mITT eyes that are ≤1 year since onset of symptoms at BL and have the Month 12 assessment. External NH control set is generated as described in section 8.5.1 (Matching algorithm for the primary endpoint), using VA assessments within 12±3 months from BL.

Analysis method: The primary endpoint will be analysed using a logistic regression model. The binary response will be used as the dependent variable. The independent variables include the treatment group (Raxone® treated patients versus untreated control group), gender (male, female) and mutation group (G11778A, G3460A, T14484C) as fixed factors.

The difference between the Raxone® treated patients versus NH group will be estimated with odds ratio, two-sided 95% confidence intervals and two-sided p-values

```
proc logistic;
  class treatment gender mutation / param=ref;
  model CRB(event='1') = treatment mutation gender / link=logit clodds=pl;
  oddsratio treatment;
run;
```

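### The inverse-probability-weighted sensitivity analysis counts about twice the eyes observed, so its confidence interval is about 1.4 times too narrow on the log-odds scale

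*SAP*

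**What the plan says.** SAP Section 12.1 fits a logistic regression with three terms: "model CRB(event='1') = treatment mutation gender / link=logit clodds=pl". The odds-ratio limits are therefore profile-likelihood limits from the model.

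SAP Section 12.1.1 adds a sensitivity analysis. A propensity score is estimated from gender, mutation, age, months from symptom onset and baseline logMAR. Treated eyes then receive the weight 1/ps. The control branch of the code reads "else if treatment = 0 then ps weight = 1/(1 - ps" up to its closing bracket. The instruction for the outcome model is "The same primary model as described above will be applied with the inverse probability weight", and the code does this with the single line "weight ps_weight", keeping `clodds=pl`.

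Neither document specifies stabilised or normalised weights, truncation, a robust variance or a bootstrap for this analysis.

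**The concern.** The comparison is not randomised. The primary model adjusts for mutation and gender only. The matching in SAP Section 8.5.1 deals with time from onset, for which it claims "This algorithm will guarantee that the time from the onset of symptoms to the BL assessment is comparable". Age and baseline visual acuity are adjusted for in one planned analysis of the primary endpoint, and it is this one. The protocol's GLIMMIX sensitivity analysis (Section 9.4.2) uses factors similar to the primary model's, and the age and acuity subgroups in SAP Section 9.3 lie within LEROS.

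Anyone judging whether measured confounding explains the primary result will compare the two odds ratios and their intervals. As coded, the weighted interval will come out narrower than it should, and probably narrower than the primary one. A reader would take that as added precision when it is an effect of the weight scaling.

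**Working it through.** **Inputs.** SAP Section 6 gives 110 evaluable LEROS eyes at an assumed 40%, a control rate of 22%, and 90% power. It gives the control count as "Based on the combined data from 175 eyes in the two natural history studies". SAP Section 7 uses a two-sided 95% interval. Total N = 110 + 175 = 285.

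**The plan's own figure.** The SAP states no figure for the weighted analysis, so the sample size was checked first. With control-to-treated ratio r = 175/110 and pooled rate p̄ = (110×0.40 + 175×0.22)/285 = 0.289:

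n = [1.960√(p̄q̄(1 + 1/r)) + 1.282√(0.24 + 0.1716/r)]² / 0.18² = 110.3, which rounds up to 111.

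Power at 110 eyes is 89.9%. The stated 110 is reproduced, and the four inputs fit together.

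**Sum of the weights.** Take a constant score ps = 110/285 = 0.386.
- Treated: 110 × 285/110 = 285.
- Control: 175 × 285/175 = 285.
- Total: 570 = 2N.

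With estimated, varying scores the same holds on average. In simulation the sum divided by N was 2.00 in every setting.

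**Effect of scaling alone.** Multiplying all weights by a constant c leaves the odds ratio unchanged and divides the model-based variance by c. Going from a sum of N to 2N shrinks the log-odds-ratio SE by √2 = 1.414. Coverage of a nominal 95% interval becomes 2Φ(1.96/1.414) − 1 = 83.4%, so a nominal 5% test rejects 16.6% of the time.

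**At the planning figures** (constant weights within group, independent eyes):
- Valid variance of the log odds ratio: 1/(110×0.24) + 1/(175×0.1716) = 0.0379 + 0.0333 = 0.0712; SE 0.267.
- Variance as coded: (1/0.24 + 1/0.1716)/285 = (4.167 + 5.828)/285 = 0.0351; SE 0.187.
- SE ratio: √(0.0712/0.0351) = 1.42; coverage 2Φ(1.96/1.425) − 1 = 83.1%.
- Odds ratio: (0.40/0.60)/(0.22/0.78) = 2.36. Valid 95% interval 1.40–3.99; as coded 1.64–3.41. Profile-likelihood limits, the type requested, are almost the same: 1.40–4.00 and 1.64–3.43.

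In the same closed form with control at 22%, LEROS rates of about 30–32% give a coded lower limit above 1 (1.04–1.15), whereas the valid limit is below 1 (0.88–0.98).

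**Simulation with varying weights.** Covariate distributions, imbalance and prognostic strength are assumptions, because the documents do not give them. The true odds ratio was 1 and there were 285 eyes.
- Independent eyes, 1000 replicates per setting: true SD over coded SE was 1.46–1.48 with no imbalance and 1.53–1.60 with imbalance. The nominal 5% test rejected 17.8–22.2% as coded and 4.0–5.5% with a sandwich variance.
- Independent eyes, 2000 replicates, covariate shifts of 0, 0.3 and 0.6 SD: ratios 1.50, 1.56 and 1.73; coverage 80%, 80% and 76%. With baseline acuity also prognostic (log odds ratio 0.4–1.2 per SD), the ratio ran from 1.35 to 1.80.
- Weights normalised to N with the model SE kept, same three shifts: coverage 94.6%, 93.0% and 89.4%.
- The coded SE was below the primary model's SE in every run, by a factor of 1.45–1.52.

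**Fellow-eye correlation, kept separate.** Adding an assumed latent correlation of 0.3–0.7 raises the ratio to 1.64–2.06 (coverage 66–77%). The same correlation gives 1.08–1.25 in the unweighted primary model, so this part is not specific to the weighted analysis.

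**The case against.** The defect itself is hard to dispute; the fair objections concern size, remedy and importance.

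- **The inputs are not final counts.** The 110 is a planning requirement and the 175 comes from the responder-rate check. Constant weights are the case in which weighting adjusts nothing. This stands: the intervals above illustrate the scaling and do not forecast the result.
- **The factor is not a floor and depends on the scale.** √2 applies to the log odds ratio. On the odds-ratio scale the two intervals differ in width by 2.59/1.77, about 1.46. Baseline acuity is part of the endpoint definition, so it may well be prognostic, and the ratio then fell as low as 1.35. This stands, but every setting examined shows material understatement.
- **Clustering belongs to the primary model.** An unclustered sandwich restores coverage when eyes are independent (94.6–96.8% in one check). That is correct for the weight-specific error. Clustering on patient is still a valid robust variance; the consequence is that SEs can be compared only if both models use the same estimator.
- **Stabilising is partly preference.** Under a robust variance, overall rescaling does not alter the interval. True, but normalising without a robust variance is not a reliable substitute once groups differ.
- **The analysis is supportive.** The superiority rule in SAP Section 7 ("Superiority is shown if the lower limit of the two-sided 95% CI is greater than 1") is not attached to it. However, SAP Section 9 says generally "In the statistical analyses a p-value less than 0.05 will be considered as statistically significant", so its p-value would be read against 0.05.
- **Software behaviour is not in the documents.** That an unnormalised WEIGHT statement uses weights as supplied is standard for PROC LOGISTIC, and the code asks for nothing else.

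**Conclusion.** The concern holds. As coded, the confidence interval and p-value of the weighted sensitivity analysis are not valid. The √2 understatement of the log-odds-ratio SE, relative to weights summing to N, follows from the weights summing to 2N and needs no assumption about overlap or covariates. The total understatement does depend on such assumptions: 1.42 at the planning figures, and 1.35–1.80 across the simulated settings with independent eyes. Fellow-eye correlation would add to this but is a shared problem.

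The weighted odds ratio, and its shift from the primary estimate, remain informative. The primary analysis and the trial's type I error are not affected. The change should be made because this analysis is the SAP's main check on measured confounding by age and baseline acuity.

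**What to change.** In SAP Section 12.1.1, fit the weighted model with a robust variance clustered on patient, for example PROC SURVEYLOGISTIC with CLUSTER and WEIGHT, or PROC GENMOD with REPEATED SUBJECT=patient and WEIGHT. A bootstrap that resamples patients and re-estimates the propensity score each time is an alternative. Use stabilised weights, and take the interval from the robust variance or bootstrap instead of `clodds=pl`.

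Normalising the weights alone is not enough: in simulation it gave 89–95% coverage with independent eyes and 82–92% with correlated eyes. The patient-clustered sandwich gave 93–95%, and 93–97.5% when baseline acuity was prognostic.

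The cost is a few lines of SAP text and code and a wider sensitivity interval. The weighted odds ratio stays essentially the same.
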